10.3 Sample Size Considerations

A total of 2700 deaths will be observed in order to exclude a hazard ratio (darbepoetin alfa to placebo) of 1.15 with a 1-sided significance level of 0.025. With 2700 deaths, the study is powered at just over 90% if the true hazard ratio is 1.0 (approximately, 93%). To observe 2700 deaths, the study will randomize a total of 3000 subjects which assumes a 7-year enrollment period, a 3-year follow-up after last subject enrolled, a 1-year survival rate of 51% (Sandler et al, 2006), and a common exponential drop-out rate of 0.0511.

Excluding a hazard ratio of 1.15 corresponds to excluding a decrease in median survival of approximately 1.6 months in the darbepoetin alfa arm group compared to placebo.

This estimation assumes survival time is exponentially distributed which allows for a conversion from a hazard ratio to medians. A median survival of 12.3 months (Sandler et al, 2006) was assumed as the median survival in the placebo arm in order to derive the difference in medians that correspond to a hazard ratio of 1.15.

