3.1 Study Design

This is a double-blind, randomized, placebo-controlled, phase 3 study in CIA subjects receiving multi-cycle chemotherapy for the treatment of advanced stage NSCLC cancer. Randomization will occur in a 2 to 1 ratio (darbepoetin alfa to placebo) and will be stratified by histology (squamous versus other), screening hemoglobin (< 10.0 g/dL versus \geq 10.0 g/dL), and geographic region (see Section 4.1 for regions).

Subjects will receive IP Q3W during the treatment period. IP will be discontinued within 3 weeks after the completion of chemotherapy, or upon the determination of disease progression, whichever occurs first. Study visits Q3W and imaging studies Q9W will occur during the treatment period until disease progression.

An end of the treatment period visit will occur at the next Q3W visit after disease progression has been determined. **Hemoglobin and other hematology and chemistry values collected beyond this period (ie, beyond 3 weeks after disease progression) will be excluded from analysis.** Subjects will then enter long term follow-up and will be followed for survival until death, until approximately 2700 deaths have occurred **or until early study termination**.

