Progression- free Survival	Summarize the number of subjects with events and numbers of subjects censored, Kaplan-Meier quartiles, KM estimates of 1-year, 2-year, and 3-year survival by treatment group. Present the hazard ratio with 95% confidence interval Dataset: Radiographic Endpoint Primary Analysis Set	•	KM time-to-event plots using the Radiographic Endpoint Dataset: Radiographic Endpoint Primary Analysis Set Repeat analysis by stratification factors Dataset: Radiographic Endpoint Primary Analysis Set

		•	Repeat analysis using Radiographic Endpoint Full Analysis set Repeat analysis using Per Protocol Analysis set Repeat analysis for subjects impacted vs not impacted by early study termination Dataset: Radiographic Endpoint Primary Analysis Set
Progression- free Survival	Cox proportional hazards regression modelling with treatment group in the model, stratified by the stratification factors. This will include the p-value testing for an interaction between treatment group and each stratification factor Dataset: Radiographic Endpoint Primary Analysis Set	•	Cox proportional hazards regression modelling including treatment group only. Dataset: Radiographic Endpoint Primary Analysis Set Cox proportional hazards regression modelling including the stratification factors and other clinically important covariates Dataset: Radiographic Endpoint Primary Analysis Set
Progression- free Survival with Adjustment for Cross-in	Summarize the results of a Cox regression that estimates the hazard ratio with treatment group treated as a time-dependent covariate to account for cross-in of erythropoietic agent use by placebo Dataset: Radiographic Endpoint Primary Analysis Set		
Progression- free Survival to account for RECIST version	Summarize the results of a Cox regression that estimates the hazard ratio with treatment group treated and RECIST version as covariates Dataset: Radiographic Endpoint Primary Analysis Set		
Other Safety En	dpoint		
Time to disease progression	Summarize the number of subjects with events and numbers of subjects censored, Kaplan-Meier quartiles, KM estimates of 1-year, 2-year, and 3-year survival by treatment group. Present the hazard ratio with 95% confidence interval. Dataset: Radiographic Endpoint Primary Analysis Set	•	Repeat analysis by stratification factors Dataset: Radiographic Endpoint Primary Analysis Set KM time-to-event plots using the Radiographic Endpoint Dataset: Radiographic Endpoint Primary Analysis Set

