9.6.1 Primary Safety Endpoints

The primary analysis of OS will be based on the primary analysis set and will use a Cox regression model, stratified by the randomization factors, with treatment group as the only covariate. Subjects last known to be alive will be censored on date of last contact. Non-inferiority will be declared if the upper confidence limit for the hazard ratio (darbepoetin alfa to placebo) is less than 1.15 using a 1-sided significance level of 0.025.

The following sensitivity analyses will be performed as further exploratory analyses for the primary endpoint:

- To provide a completely unadjusted analysis, a hazard ratio with 95% confidence interval will be estimated from an unstratified Cox regression with treatment group as the only covariate.
- To support the results obtained from the primary analysis set, analyses will be performed using the overall survival per protocol set.
- To explore the consistency of the treatment effect, Cox regression models will be generated including the stratification variables and covariates listed in Section 4.1. These models will include any interaction terms with treatment group where nominal p-values of <0.10.
- In addition, a hazard ratio with 95% confidence interval will be generated from an unstratified Cox regression for each stratum formed from the combination of randomization factors (e.g., subjects from North America with squamous cell and who have a screening hemoglobin < 10.0 g/dL) and for each level of a given stratification factor (e.g., subjects from North America).

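### Hazard ratios for single levels of a stratification factor are planned from an unstratified Cox model that omits the other two randomization factors: a small inconsistency, free to remove

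*SAP*

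**What the plan says.** The primary overall survival (OS) analysis in SAP 9.6.1 "will use a Cox regression model, stratified by the randomization factors, with treatment group as the only covariate". The factors are histology, screening hemoglobin and geographic region (SAP 3.1 and 4.1). SAP 9.1 takes their values from the IVRS for stratified analyses.

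The same section lists sensitivity analyses, labelled exploratory. One of them gives a hazard ratio and 95% confidence interval that "will be generated from an unstratified Cox regression for each stratum formed from the combination of randomization factors", and also "for each level of a given stratification factor", with subjects from North America as the example. The word unstratified governs both parts. A separate bullet plans one overall unstratified hazard ratio as an unadjusted analysis.

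SAP 9.6.2 says that sensitivity analyses for progression-free survival (PFS) will resemble those for OS. The safety endpoint summary table in SAP 9.6 has rows repeating the OS and PFS analyses by stratification factor, without naming the model. It also has a PFS row for RECIST version, from a Cox model that "estimates the hazard ratio with treatment group treated and RECIST version as covariates". That row does not say whether the model is stratified.

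**The concern.** One model is prescribed for two different tasks. In a full cell all three factors are constant, so an unstratified model is appropriate. In a single level, for example all subjects with screening hemoglobin below 10 g/dL, histology and region still vary and are ignored.

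Omitting prognostic factors from a Cox model moves a non-null hazard ratio towards 1 even when randomization balances them. The per-level hazard ratios will be read beside the primary one, so part of any difference could come from the change of model and not from the subgroup. SAP section 12 puts OS by region, histology and screening hemoglobin among the first outputs after database lock. If that means results by level, they will be seen early and next to the primary result.

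**Working it through.** **1. Reproduce the plan's own figures.** Protocol 10.3 states: "A total of 2700 deaths will be observed in order to exclude a hazard ratio" "of 1.15 with a 1-sided significance level of 0.025", and: "With 2700 deaths, the study is powered at just over 90% if the true hazard ratio is 1.0", with about 93% given. Allocation is 2:1, so the variance factor is (2/3)(1/3) = 2/9.

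- z = √(2700 × 2/9) × ln 1.15 − 1.960 = 24.495 × 0.13976 − 1.960 = 1.463, so power = 92.8%, against about 93% stated. With 1:1 allocation it would be 95.3%, which does not match.
- Difference in medians: 12.3 − 12.3/1.15 = 1.60 months, as stated.
- Expected deaths from 3000 subjects, with λ = −ln 0.51 = 0.6733 per year, drop-out η = 0.0511 (taken as per year), and follow-up u uniform on 3 to 10 years: 3000 × mean of [λ/(λ+η)] × [1 − exp(−(λ+η)u)] = 2726, against 2700 planned.

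**2. Inputs that the documents do not give.** No prevalence or prognostic strength is stated for the factors. Assumed: 40% squamous, 45% with hemoglobin below 10 g/dL, and six equal regions (Japan is analyzed with Region 3) with equally spaced log hazards. Assumed hazard ratios for histology / hemoglobin / highest-to-lowest region: 1.2/1.2/1.2 (mild), 1.3/1.3/1.5 (moderate), 1.5/1.5/2 (strong), 2/2/3 (extreme).

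**3. Large-sample value of the unstratified estimate.** For arm a with conditional hazard ratio h_a (1 for placebo), Y_a(t) = C(t) Σ p_k exp(−λ m_k h_a t) and D_a(t) = C(t) Σ p_k λ m_k h_a exp(−λ m_k h_a t). Here p_k and m_k are the share and relative hazard of each omitted-factor combination, m_k has geometric mean 1, and C(t) is the drop-out and accrual censoring of step 1. With π = 2/3, the Cox estimate converges to exp(b), where b solves

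∫ { πD₁ − [πD₁ + (1−π)D₀] × πY₁eᵇ / [πY₁eᵇ + (1−π)Y₀] } dt = 0.

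| Conditional HR | Model | Mild | Moderate | Strong | Extreme |
|---|---|---|---|---|---|
| 1.15 | hemoglobin level (histology, region omitted) | 1.148 | 1.145 | 1.139 | 1.126 |
| 1.15 | region level (histology, hemoglobin omitted) | 1.148 | 1.146 | 1.141 | 1.128 |
| 1.15 | overall unstratified (all three omitted) | 1.147 | 1.143 | 1.135 | 1.119 |
| 1.15 | single full cell | 1.150 | 1.150 | 1.150 | 1.150 |
| 1.00 | any of these | 1.000 | 1.000 | 1.000 | 1.000 |
| 0.85 | hemoglobin level | 0.851 | 0.854 | 0.859 | 0.870 |

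At 1.15 the hemoglobin-level shift is 0.002, 0.005, 0.011 and 0.024. On the log scale that is a loss of about 1%, 3%, 7% and 15%.

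**4. Cross-check by simulation.** With n = 400,000, true hazard ratio 1.15, 2:1 allocation and about 85% deaths, region and hemoglobin were omitted (the histology-level case). Region log-hazard SD was 0.25 to 0.40 and the hemoglobin hazard ratio 1.3 to 1.6, both assumed. Unstratified against stratified gave 1.141 against 1.148, and 1.133 against 1.153; the Monte Carlo standard error of the log hazard ratio was about 0.004. Six equally spaced regions with ratio r have SD 0.342 × ln r, which is 0.24 at r = 2 and 0.38 at r = 3. These settings therefore correspond roughly to the strong and extreme region effects above, and the results agree in direction and order.

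**5. Compare with sampling error.** SE(log HR) = 1/√(D × 2/9), and the 95% interval multiplies and divides the estimate by exp(1.96 SE).

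- Half of 2700 deaths, D = 1350: SE 0.058, factor 1.12.
- One sixth, D = 450: SE 0.100, factor 1.22.
- One of 24 equal cells, D = 112.5: SE 0.200, factor 1.48.

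In the strong case, a level with half the deaths shifts by ln 1.15 − ln 1.139 = 0.0097, about one sixth of its standard error. SAP 3.2 reports that the study stopped with 2549 subjects, so fewer than 2700 deaths are possible and the real intervals will be wider.

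**The case against.** A less adjusted hazard ratio is not an error. It answers a slightly different question, and an unstratified estimate per subgroup level is a legitimate descriptive choice. These analyses are exploratory with no decision rule, and the shift sits well inside sampling error. All of that stands, and it limits the point to a low-severity improvement. It does not explain why the primary model keeps the factors and the per-level model leaves them out.

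Four stronger readings are tempting, and the documents do not support them.

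- **That the per-level results cannot be compared with the primary one.** The shift is too small for that. The planned overall unstratified hazard ratio is also a close reference, though not exact: it omits three factors instead of two, and the SAP does not direct the reader to it.
- **That consistency across subgroups rests on these estimates.** SAP 9.6.1 explores consistency with models that include the stratification variables and the Section 4.1 covariates, plus treatment interactions at a nominal p below 0.10. The summary table adds interaction tests within the stratified model. The per-level hazard ratios are an addition to these.
- **That the shift favours darbepoetin alfa.** It does so only if the conditional hazard ratio exceeds 1. Below 1 it works against the drug, and the non-inferiority rule is not applied to these estimates.
- **That the RECIST-version PFS model drops the randomization factors.** Its table row is silent. The OS cross-in row is equally silent, yet the text of SAP 9.6.1 specifies a stratified regression for it. Where the SAP intends no stratification elsewhere, it says unstratified or treatment group only. Still, no text settles the RECIST covariate model as it does the cross-in model, so a clarification is warranted.

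**Conclusion.** The point holds in a limited form, at low severity. Hazard ratios for single levels of a stratification factor come from a model that omits the other two randomization factors, although the primary model stratifies on all three. A non-null estimate is therefore pulled slightly towards 1.

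At a conditional hazard ratio of 1.15 the pull is about 0.01 or less for mild to strong prognostic effects and about 0.024 in a deliberately extreme case. It is zero at 1.0, the value assumed for power. These sizes rest on assumed prevalences and prognostic strengths, a constant conditional hazard ratio and exponential survival. Full-cell estimates, the primary non-inferiority test, alpha and power are not touched.

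**What to change.** In SAP 9.6.1, separate the two tasks. Keep the unstratified Cox model for full cells and for the planned overall unadjusted analysis. For each single level of a stratification factor, fit the Cox model with treatment as the only covariate, stratified by the remaining two randomization factors with IVRS values. Say in SAP 9.6.2 that the parallel PFS analysis does the same.

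In the RECIST-version row of the safety endpoint summary table, state that the model is stratified by the randomization factors.

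The cost is a few words in the SAP and one strata statement per model. A region level would have at most 4 strata (2 × 2), and a histology or hemoglobin level at most 12 (6 × 2). SAP 4.1 already allows regions to be combined if some are sparse.

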9.6.2 Secondary Safety Endpoint

The primary analysis of PFS will be based on the radiographic endpoint primary analysis set and will use a Cox regression model, stratified by the randomization factors, with treatment group as the only covariate. PFS will be measured from randomization to disease progression (as defined by the version of RECIST specified in the protocol at the time of subject enrollment) or death from any cause; subjects without either event will be censored at the last disease assessment date. If non-inferiority has been declared for OS, non-inferiority will be declared for PFS if the upper confidence limit for the hazard ratio is less than 1.15 using a 1-sided significance level of 0.025.

Sensitivity analyses for PFS will be done similar to those for the primary endpoint, OS, as further exploratory analyses for the secondary endpoint: However, the sensitivity analyses will be largely limited to the Radiographic Endpoint Primary Analysis Set (ie, few sensitivity analyses using the Per Protocol Analysis Set or any other data set are planned). In addition, a sensitivity analysis may be performed that examines the treatment effect by subgroups formed on the basis of which version of RECIST was used to evaluate the subject. If this analysis is performed, however, the results will need to be interpreted cautiously since the version of RECIST will be confounded with time of enrollment (RECIST 1.0 subjects will be enrolled first, RECIST 1.1 subjects second) and it is anticipated that less than 10% of the subjects will be evaluated with RECIST 1.0.

9.6.3 Other Safety Endpoints

The number and percentage of subjects with a confirmed objective tumor response **rate** (as defined by the version of RECIST specified in the protocol at the time of subject enrollment) will be presented by treatment group. Subjects without any post-baseline tumor assessments will be considered non-responders. Subjects without measurable disease at baseline will be excluded from the analysis. To assess treatment group differences, the Cochran-Mantel-Haenszel method will be used which will adjust for the stratification factors at randomization.

In addition, a more detailed classification of response will be presented by summarizing the number and percentage of subjects whose best overall response during the study falls into each of the following categories: complete response, partial response, stable disease, disease progression, not evaluable, missing due to clinical progression, and missing for reasons other than clinical progression. **Non-response will also be summarized.** These analyses will be performed for the **radiographic endpoint** primary analysis set.

9.6.4 Adverse Events and Disease-related Events

The Medical Dictionary for Regulatory Activities (MedDRA) version **20.0** or later will be used to code all adverse events to a system organ class and a preferred term. **Treatment-emergent adverse events are events with an onset after the administration of the first dose of investigational product.** The subject incidence of adverse events will be summarized for all treatment emergent adverse events, serious adverse events, adverse events leading to withdrawal of investigational product, fatal adverse events and adverse events of interest using the safety analysis set. Subject incidence of all treatment-emergent adverse events, serious adverse events, adverse events leading to withdrawal of investigational product, and fatal adverse events will be tabulated by system organ class and preferred term in alphabetical order.

Subject incidence of events of interest will also be summarized according to their categories and preferred term within category. Special interest adverse events include TVEs, VTEs and AEs associated with RBC transfusions. All three sub-categories of TVEs (VTEs, ATEs, and unspecified/mixed thromboembolic events)

will be summarized in order to present the complete decomposition of TVEs. However, ATEs alone are not of special interest. The primary analysis of VTEs will include fatal VTEs and VTEs confirmed by imaging; a sensitivity analysis will summarize all VTEs regardless of severity or confirmation.

In addition, summaries of treatment emergent and serious adverse events occurring in at least 5% of the subjects by preferred term in any treatment arm will be provided in descending order of frequency in the darbepoetin alfa arm. Summaries of treatment-emergent and serious adverse events will also be tabulated by system organ class, preferred term and grade. All adverse event tables will be summarized by treatment group using the safety analysis set. In addition, serious adverse events, events of interest and VTE data will be analyzed using the primary analysis set.

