EpoR	Erythropoietin receptor
ESA	Erythropoiesis stimulating agent
FDA	Food and Drug Administration
FDG-PET	Fluorodeoxyglucose-PET
g/dL	Gram per deciliter
GBG	German Breast Group
GGT	Gamma-glutamyltransferase
GOG	Gynecologic Oncology Group
HIV	Human immunodeficiency virus
HR	Hazard ratio
HSA-free	Human serum albumin-free
ICF	Informed consent form
ICH GCP	International Conference on Harmonisation Tripartite Guideline on Good Clinical Practice
ID	Identification
IEC/IRB	Independent ethics committee/institutional review board
IP	Investigational product
IV	Intravenous
IVR/IWR System	Interactive Voice Response/Interactive Web Response System
PPD	
kg	Kilogram
LDH	Lactate dehydrogenase
LTFU	Long-term follow-up
MCH	Mean corpuscular hemoglobin
MCHC	Mean corpuscular hemoglobin concentration
MCV	Mean corpuscular volume
MDS	Myelodysplastic syndromes
mL	Milliliter
MRI	Magnetic resonance imaging

Abbreviation or Term	Definition/Explanation
NA	Not applicable
NE	Inevaluable
ng	Nanogram
NSCLC	Non-small cell lung cancer
ODAC	Oncologic Drug Advisory Committee
OR	Odds ratio
OS	Overall survival
PD	Progressive disease
PE	Physical examination or pulmonary embolism
PET	Positron emission tomography
PET-CT	Positron emission tomography-computer tomography
PFS	Progression-free survival
pg	Picogram
PICC	Peripherally-inserted central catheter
PIN	Personal identification number
PR	Partial response
Q3M	Once-every-3-months
Q3W	Once-every-3-weeks
Q9W	Once-every-9-weeks
QW	Once-weekly
RBC	Red blood cell
RECIST	Response evaluation criteria in solid tumors
rHuEPO	Recombinant human erythropoietin
SAE	Serious adverse events
SAER	Serious adverse event report
SCLC	Small cell lung cancer
Screening hemoglobin	Local laboratory hemoglobin; sample obtained within 7 days prior to randomization
Screening period	Starts when the subject signs and dates the informed consent form and ends when the subject is randomized or screen failed. Must not exceed 21 days.
SD	Stable disease
SUSAR	Suspected unexpected serious adverse reactions
TIA	Transient ischemic attack
TIBC	Total iron binding capacity
Tsat	Transferrin saturation

Abbreviation or Term	Definition/Explanation
Treatment period	Starts when the subject is randomized and ends at the next Q3W visit after disease progression has been determined (EOTP). Note that EOTP is based on disease progression, not IP dosing.
TVE	Thrombovascular event
μg	microgram
ULN	Upper limit of normal
US	Ultrasound
VTE	Venous thromboembolic event
WBC	White blood cell
Wk	Week

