- If hemoglobin increases by > 1.5 g/dL in any 21 day period in the absence of RBC transfusion, the IVR/IWR System will reduce the dose of IP by approximately 40% of the previous dose (ie, 500 μg to 300 μg; 300 μg to 200 μg, 200 μg to 100 μg) for a maximum of 3 dose reductions. Investigational product will be discontinued after 3 dose reductions.
- If hemoglobin > 12.0 g/dL, the IVR/IWR System will instruct the investigator that IP will be temporarily withheld until hemoglobin falls to ≤ 12.0 g/dL at which time treatment will be restarted at a dose which is reduced by approximately 40% of the previous dose (ie, 500 µg to 300 µg; 300 µg to 200 µg, 200 µg to 100 µg) for a maximum of 3 dose reductions. Investigational product will be discontinued after 3 dose reductions.

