7.1.8 Thrombovascular Events

All subjects will be monitored closely for clinical signs and symptoms of thrombovascular events (TVE) (arterial thromboembolic events [ATE]: stroke, transient ischemic attack

[TIA], acute coronary syndromes [ACS], other arterial thrombosis/embolism; venous thromboembolic events [VTE]: deep vein thrombosis [DVT], pulmonary embolism [PE], other venous thrombosis excluding superficial venous thrombosis). If any signs or symptoms are present, the subject will undergo specific laboratory and medical imaging studies to confirm VTEs. The medical imaging study or studies selected will depend on the anatomic site of the suspected VTE or organ of involvement (eg, Doppler ultrasound, venography, ventilation perfusion lung scan, angiography, MRI). If a VTE is confirmed, appropriate medical care according to standard local clinical practice should be initiated immediately.

TVEs will be documented in the CRF through the EOTP or 30 days after the last dose of IP, whichever occurs later.

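### VTEs and other TVEs are compared only as crude subject percentages, while the VTE window closes after progression; if progression differs by arm, the crude ratio is biased in either direction

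*SAP*

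**What the plan says.** **Analysis.** For events of interest, which include TVEs, VTEs and transfusion-associated AEs, SAP 9.6.4 states: "Subject incidence of events of interest will also be summarized according to their categories and preferred term within category". The matching rows of the safety endpoint table in SAP 9.6 are tabulations of subjects by arm, in the safety set and, for several rows, again in the primary analysis set. The primary VTE summary takes fatal and imaging-confirmed events, and its sensitivity analysis drops the confirmation requirement. No person-time rate, time-to-first-event analysis, competing-risk method or between-arm confidence interval is stated. SAP 9.6.10 summarises IP duration but does not use it as a denominator for events.

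**Window.** Protocol 7.1.8 sets the collection period: "TVEs will be documented in the CRF through the EOTP or 30 days after the last dose of IP, whichever occurs later". The Study Glossary adds, under the treatment period: "Note that EOTP is based on disease progression, not IP dosing". EOTP is the next Q3W visit after progression, or an earlier visit for subjects who cannot continue visits and imaging.

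**Three versions of the window.** Protocol 7.1.8 and 7.1.10 apply the longer window to all TVEs. The treatment-emergent definition in SAP section 5 extends it only for VTEs and transfusion-associated AEs. On that wording, arterial and unspecified/mixed TVEs stop counting 30 days after the last dose. SAP 9.6.4 defines treatment-emergent by onset after the first dose and gives no end date.

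**The concern.** A percentage of subjects with an event compares two arms fairly only if both are watched for similar lengths of time. Here the length of observation is mainly set by progression, a component of the secondary endpoint PFS, and protocol 2.2.2 describes the effect of ESAs on PFS as uncertain. Protocol 2.2 describes the thromboembolic risk of ESAs as well documented, so this is the harm on which readers will most want a reliable between-arm figure. Time to progression gets a hazard ratio with a confidence interval and tumor response gets a stratified test, but VTE gets neither.

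If darbepoetin subjects progressed or died sooner, fewer of their VTEs could be recorded and the crude ratio would understate the effect. If they progressed later, it would overstate it.

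**Working it through.** **1. The plan's own figure.** The documents state no figure for VTE. The design figure checks the allocation and margin used below. The protocol says: "A total of 2700 deaths will be observed in order to exclude a hazard ratio (darbepoetin alfa to placebo) of 1.15". The test is at the one-sided 2.5% level, and the stated power is about 93%. With 2:1 allocation, z = ln(1.15) × √(2700 × 2/3 × 1/3) − 1.96 = 0.1398 × 24.49 − 1.96 = 1.46, so power is 92.8%. This reproduces.

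**2. Inputs for the window effect.**
- From the documents: the window rule above; 2549 subjects (SAP 3.2), about 1699 and 850 at 2:1; the PFS margin of 1.15 (SAP 9.6.2), used as a scenario and not as an expected effect.
- Assumed: exponential PFS with placebo median m = 4 to 6.5 months; a tail of g = 0.7 or 1.0 month from progression to window end; 15% of PFS events are deaths, which close the window at once; constant VTE hazard h; placebo crude incidence 5% or 8%; true VTE hazard ratio 1.5.

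**3. Simplest version, no tail.** Crude incidence = v/(v + r), with v = 0.01 per month on placebo and r = ln 2/6 = 0.1155 per month.
- Placebo: 0.01/0.1255 = 7.97%.
- Darbepoetin, equal PFS: 0.015/0.1305 = 11.49%; ratio 1.44.
- Darbepoetin, PFS hazard ratio 1.15: 0.015/(0.015 + 0.1329) = 10.15%; ratio 1.27.

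**4. With the tail.** Let l be the PFS hazard, ln 2/m on placebo. Crude incidence = 1 − [l/(l + h)] × [0.15 + 0.85 exp(−hg)]. Mean window, ignoring VTE, = 1/l + 0.85g.

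Example with m = 5, g = 0.7 and placebo incidence 8%: l = 0.1386 and h = 0.01107.
- Darbepoetin, h = 0.0166, equal PFS: 1 − 0.8930 × 0.9902 = 11.57%; ratio 1.45.
- Darbepoetin, l = 0.1594 (PFS hazard ratio 1.15): 1 − 0.9057 × 0.9902 = 10.32%; ratio 1.29.
- Mean window: 7.21 + 0.60 = 7.81 months against 6.27 + 0.60 = 6.87 months, 12% shorter.

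Over the whole grid, for a true VTE hazard ratio of 1.5:

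| PFS hazard ratio | Crude VTE ratio | Power of crude comparison (2-sided 0.05) |
|---|---|---|
| 0.9 | 1.57–1.61 | not needed |
| 1.0 | 1.45–1.47 | 62%–81% |
| 1.15 | 1.29–1.31 | 31%–49% |
| 1.3 | 1.16–1.19 | not needed |

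**5. How much would mask the effect completely?** A crude ratio of 1.0 needs a PFS hazard ratio of 1.16–1.18 for a true VTE hazard ratio of 1.15, 1.33–1.36 for 1.3, and 1.55–1.63 for 1.5.

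**6. Other direction.** With no true VTE effect and a PFS hazard ratio of 0.85, the crude ratio is about 1.15.

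**7. Early risk.** If VTEs occur only in the first 4 months (g = 0.7, placebo incidence 8%), a true 1.5 shows as 1.47 with equal PFS and 1.42–1.44 at a PFS hazard ratio of 1.15.

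**8. Rates per subject-time.** Take a placebo hazard of 2% per month for 4 months and none after, a true hazard ratio of 1.5, m = 6, a 0.7-month tail for all subjects and a PFS hazard ratio of 1.15. Incidence is 6.64% against 9.58%, and mean time at risk is 8.78 against 7.50 months. The crude ratio is 9.58/6.64 = 1.44. The rate ratio is (9.58/7.50)/(6.64/8.78) = 1.69, further from 1.5 than the crude ratio.

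**The case against.** **These points stand.**
- The bias has no fixed sign. The NSCLC chemotherapy row in protocol Table 3 that reports a progression hazard ratio gives 0.91 (0.68, 1.23). That would point, if anything, toward an inflated VTE ratio.
- A PFS hazard ratio of 1.15 is the margin, not a forecast.
- IP stops within 3 weeks of the last chemotherapy dose, so an excess VTE risk may well come early. The distortion is then small (step 7).
- Unequal windows would be visible. SAP 9.2 plots discontinuation from the treatment period by reason and arm, and PFS, time to progression and IP duration are reported by arm. A reader could see the imbalance but could not correct the VTE comparison for it.
- These endpoints lie outside the testing hierarchy, and any test on them is descriptive. Fatal VTEs also count in OS, which is followed past EOTP.
- The protocol's other safety endpoints and its section 10.6.2.3 are redacted, so more detail may exist there. The point rests on the SAP.

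**A tempting argument that fails for VTEs.** A reader might infer that the hemoglobin rules shorten the darbepoetin VTE window, since "Investigational product will be discontinued after 3 dose reductions". They cannot make it close before EOTP, because the window runs to the later of two dates. They could matter only for arterial and unspecified/mixed TVEs, and only on the SAP's narrower wording.

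**Conclusion.** The concern holds as one of possible bias in a descriptive safety comparison. VTE follow-up depends on a post-randomisation outcome that may differ by arm, and the only planned measure ignores follow-up time. Under constant hazards, a PFS hazard ratio of 1.15 takes a true VTE hazard ratio of 1.5 from a crude 1.44–1.47 down to 1.27–1.31 and cuts the power of the crude comparison substantially. With early risk the loss is minor. The VTE rates, PFS medians, hazard ratios and 15% death share are all assumptions, because the documents give none of them.

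A reader might go further and infer that the VTE window ends at progression and that the crude percentages would hide the harm. The documents do not support either step. The window runs to the Q3W visit after progression, or to 30 days after the last dose if later. Complete masking would need a PFS hazard ratio about as large as the VTE hazard ratio itself. Nor do they show that darbepoetin speeds progression: protocol 2.2.2 calls the effect uncertain.

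**What to change.** 1. **SAP 9.6.4 and the VTE and events-of-interest rows.** Keep the percentages. For the primary VTE definition (fatal or imaging-confirmed) and for all TVEs, add time from study day 1 to first event over the collection window. Report a cause-specific Cox hazard ratio with 95% CI, stratified as for OS and censored at death or window end, and cumulative incidence curves by arm with death as a competing event.
2. **Subject-year rates** may be added as a supplement, with a note that they assume a constant hazard and can overstate harm when risk is early (step 8). They should not lead.
3. **Reconcile the windows.** Protocol 7.1.8 and 7.1.10, the exception in SAP section 5, and the open-ended definition in SAP 9.6.4 should give one stated window for all TVEs.

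The cost is SAP wording and two or three descriptive outputs from dates already collected. No visit or procedure changes, and the testing hierarchy is untouched. Two limits remain and should be stated with the results: events after the window are not systematically recorded and cannot be recovered, and censoring at window end treats that closure as uninformative about later VTE risk.
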